#### 15.6.2 Final Analyses of Efficacy Endpoints

The primary efficacy analysis on PFS will be performed when approximately 280 PFS events and 128 OS events have occurred. This is estimated to occur approximately 48 months after the first patient is randomized. Allos will set a data cut-off date for the primary efficacy analyses in anticipation of 280th PFS event and 128th OS event. The primary efficacy analysis on OS will be performed when approximately 385 OS events have occurred.

A step-down procedure will be used for analyzing the co-primary endpoints of PFS and OS. If the PFS endpoint is significant at the 0.05 level the OS endpoint will be tested at an overall significance level of 0.05. However, if the PFS endpoint fails to show significance, the study will be stopped and OS will not be tested. The study will meet its primary objective if both the PFS and OS endpoints are significant. The interim analysis for OS will be implemented using the error-spending approach of Lan and DeMets according to the unified family approach with boundary relationships of O'Brien and Fleming for early stopping to reject the null hypothesis (superiority). The boundaries for early stopping due to failure to reject the null hypothesis (futility) will be determined according to the unified family approach with boundary shape parameters on the sample mean scale that result from choosing  $P = 2.0$  (all R and A parameters in the unified family approach set equal to zero).

The primary analyses of PFS and objective response will use the central review tumor assessments per IWC without using PET. Additional analyses of PFS and response will use IWC, including PET, and investigators' assessment of response. Additional details regarding central review will be provided in the reviewer's charter.

## 15.7 Efficacy Endpoints

### 15.7.1 Progression-free Survival

PFS time is calculated as the number of days from randomization to the date of objective documentation of PD or death, regardless of cause (date of PD or death - date of randomization + 1). Patients who are alive without a disease response assessment of PD will be censored at their last disease assessment date or the date of randomization whichever is later. Date of progression will not be imputed for patients with missing tumor assessment(s) before an assessment of PD. Patients who withdraw from treatment prior to PD without withdrawing consent will be followed for disease status whenever possible, even if subsequent therapy, including transplant, has been initiated prior to documented PD per central review at least until the PFS analysis. Patients who have no response assessments after baseline will be censored at randomization.

Strata used in the analyses will be those used for study randomization (as recorded on the IRT). With this technique, the HR can be consistently estimated (assuming the proportional hazards model is correct), as the potential bias due to the asymmetric visits is removed. It also corrects for the Type I error inflation and retains the nominal study power.

The primary analysis of PFS will be based on PD as determined by independent central review blinded to treatment group assignment. A separate charter will detail specifics about central review operation and response/PD definition details. Additional analyses will use the investigators' assessment of response.

The stratified log-rank test will be the primary method used to test the hypothesis that pralatrexate extends PFS relative to observation. In addition, the stratified Cox regression model will be used to calculate the PFS (HR), along with the 95% confidence interval (CI). Results of the unstratified Cox regression model (and log-rank test) will also be presented. The proportional hazards assumption of the Cox model will be assessed.

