## 10.6 Response Evaluation

Response and progression of disease will be evaluated by using the International Workshop Criteria (IWC, [Appendix 4](#)). All responses will be evaluated by a designated, independent central review at least until the PFS analysis (see [Section 15.6.1](#)). The investigator's assessment of response will also be collected. All necessary documentation to determine response will be collected at the investigational sites and sent to the central reviewer. The first response evaluation is to occur 8 weeks ( $\pm$  1 week) after randomization. Subsequent response evaluations are to occur every 12 weeks ( $\pm$  1 week) timed from randomization through 3 years post-randomization, then every 24 weeks ( $\pm$  4 weeks) through 7 years post-randomization. Unscheduled response assessments will also be sent to the central reviewer for evaluation. Response assessments will occur until PD per central review, at least until the PFS analysis.

The following procedures/tests are to be performed for each response evaluation:

1. Radiographic imaging (use same imaging technique as pre-pralatrexate/observation screening):
  - CT of chest, neck, abdomen, and pelvis (MRI allowed if the patient cannot tolerate the IV contrast)
  - Whole body PET (base of skull to mid-thigh) if performed as per local standard of care
  - Other imaging techniques documenting disease site(s) other than chest, neck, abdomen, and pelvis, if applicable.
2. If applicable, assess cutaneous disease using medical photography (refer to Study Instructions).
3. Document disease-related findings per physical examination.
4. If the patient has a CR by imaging, a bone marrow biopsy/aspire assessment (including immunohistochemistry) must be performed to confirm CR if bone marrow biopsy/aspire results were positive or indeterminate prior to randomization to pralatrexate/observation. Once a patient's bone marrow is negative for lymphoma, the bone marrow biopsy/aspire will be repeated only when clinically indicated unless it is the patient's only site of disease.

5. A tumor biopsy may be performed if needed to confirm a response evaluation as per investigator discretion.
6. Document investigator's assessment of response.

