### 15.7.2 Overall Survival

OS time is calculated as the number of days from randomization to the date of death, regardless of cause (date of death - date of randomization + 1). Survival follow-up will continue for up to 7 years from randomization.

The stratified log-rank test will be the primary method used to test the hypothesis that pralatrexate extends OS relative to observation. In addition, the OS HR, along with 95% CIs, will be estimated via the stratified Cox model. Strata used in these analyses will be those used for study randomization (as recorded using the IRT). Results of the unstratified Cox regression model (and log-rank test) will also be presented. The proportional hazards assumption of the Cox model will be assessed.

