8.5 Efficacy Endpoints

8.5.1 Progression-free Survival

The stratified log-rank test will be the primary method used to test the hypothesis that pralatrexate extends PFS relative to observation. In addition, the stratified Cox regression model will be used to calculate the PFS HR, along with the 95% CI. Strata used in these analyses will be those used for study randomization (as recorded using the interactive response technology [IRT]). Results of the unstratified Cox regression model (and log-rank test) will also be presented. The proportional hazards assumption of the Cox model will be assessed.

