8.5.5 Sensitivity Analyses

A sensitivity analysis using the grouped survival methods of Prentice and Gloeckler may be performed on PFS time to assess the robustness of the results if there appears to be large differences in PD assessment patterns between the treatment groups.¹³

If there is substantial crossover of observation patients to pralatrexate use, a sensitivity analysis for OS may be conducted censoring such patients at the date of first pralatrexate use.

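### Protocol 15.7.1 credits the CR/PR randomization strata with removing assessment-timing bias, correcting Type I error and keeping power in the PFS analysis; stratification does none of this

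*Protocol*

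**What the plan says.** Protocol 15.7.1 states: "Strata used in the analyses will be those used for study randomization (as recorded on the IRT"). The next sentence refers back to this technique and says the HR is consistently estimated under proportional hazards because "the potential bias due to the asymmetric visits is removed. It also corrects for the Type I error inflation". It adds that the technique "retains the nominal study power". Protocol 15.5 gives one stratification factor, the investigator-assessed response (CR or PR) at the end of CHOP-based therapy.

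The primary test in 15.7.1 is an ordinary stratified log-rank test on progression dates from blinded central review. Dates are not imputed after missed assessments.

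The same strata sentence appears elsewhere without the assurances: "Strata used in these analyses will be those used for study randomization (as recorded using the IRT") for OS in Protocol 15.7.2, and "Strata used in these analyses will be those used for study randomization (as recorded using the interactive response technology [IRT"]) for PFS in SAP 8.5.1. SAP 8.5.5 adds that a grouped survival analysis by the Prentice-Gloeckler method "may be performed on PFS time to assess the robustness of the results if there appears to be large differences in PD assessment patterns" across arms.

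Protocol 10.6 sets one imaging schedule for both arms, timed from randomization: week 8, then every 12 weeks (each within 1 week either way) to 3 years, then every 24 weeks (within 4 weeks). It also says: "Unscheduled response assessments will also be sent to the central reviewer for evaluation".

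**The concern.** Stratifying on a baseline factor compares the arms separately among CR and PR patients. If scans happen earlier or more often in one arm, they do so within each stratum too, so the comparison carries the same distortion. The protocol therefore claims operating characteristics that its primary test does not have. SAP 8.5.5 foresees differing assessment patterns, a check that would be unnecessary if the claim were true.

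The test concerned is a gate. PFS is tested once at 0.05, and under Protocol 15.6.2 "if the PFS endpoint fails to show significance, the study will be stopped and OS will not be tested". A timing difference can act in either direction. Later detection on pralatrexate favours pralatrexate and inflates the false-positive rate. Earlier detection on pralatrexate works against it and costs power. A reader who trusts 15.7.1 would see no reason to examine either.

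**Working it through.** **1. The plan's power figure.** Inputs from Protocol 15.4: 280 PFS events, HR 0.67, 2:1 allocation, two-sided 0.05. By Schoenfeld's formula, power = Φ(√(D·p·(1−p))·|ln HR| − 1.96). With D = 280 and p = 2/3: √(280 × 2/9) = 7.888; 7.888 × 0.4005 = 3.159; Φ(3.159 − 1.960) = 88.5%. This agrees with the stated minimum of 80%. The formula has no term for assessment timing.

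**2. What stratification does.** The statistic is Z = ΣU_s / √ΣV_s over strata s, where U_s = Σ(d₁ − d·n₁/n) over the recorded event dates in stratum s. Here d and n are all events and all patients at risk, and d₁ and n₁ are those on pralatrexate. If recorded dates are shifted in one arm, U_s is no longer centred on zero in either stratum, and summing over CR and PR does not restore it.

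**3. Size, by simulation (8,000 trials per scenario).**
- From the documents: 549 patients, 2:1 in permuted blocks of 3 within CR/PR, uniform accrual over 54 months, the scan schedule and windows of Protocol 10.6, and censoring at the last scan. The data cut is at the 280th PFS event; the 128-death condition was not modelled.
- Assumed: 75% CR. Protocol 15.4 gives about 50% CR plus 10-20% PR, so 50/70 = 71% to 50/60 = 83% of responders.
- Assumed: exponential PFS with medians of 11.5 months (CR) and 7 months (PR). At 10 months this gives 0.75 × 2^(−10/11.5) + 0.25 × 2^(−10/7) = 0.50, matching the plan's 10-month control median.
- Assumed: unscheduled detection 1 week after progression, and all events PD.
- Monte Carlo standard error: about 0.25 point at 5% and 0.45 point at 80%.

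Stratified log-rank test, true HR 1. Pairs are the percentages of progressions found at unscheduled scans, pralatrexate/observation:

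| Scenario | Rejection | Estimated HR |
|---|---|---|
| 0/0 | 4.6% | |
| 30/30 | 5.5% | |
| 20/30 | 5.2% | |
| 20/40 | 6.2% | 0.97 |
| 40/20 | 5.8% | 1.02 |
| 0/30 | 6.5% | |
| 30/0 | 5.5% | |
| 0/50 | 8.6% | 0.94 |
| 50/0 | 8.0% | 1.06 |
| Mean gap of half a week, pralatrexate later | 8.8% | 0.93 |
| Mean gap of half a week, pralatrexate earlier | 7.8% | 1.07 |

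In the half-week rows every scan stays inside its window: one arm is scanned from −0.5 to +1 week and the other from −1 to +0.5 week. With scans exactly on schedule instead of spread over the window, 0/50 gives 12.8% and 50/0 gives 9.8%. The unstratified test is 0.2 to 0.8 point lower in these scenarios, so stratifying removes none of the excess.

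Power at HR 0.67 is 89.1% with equal timing, 91.9% at 20/40, 85.4% at 40/20 and 78.6% at 50/0.

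**4. Checks with separate code.** One check used 25% PR with twice the CR hazard, immediate unscheduled detection and 4,000 null trials per scenario. Stratified and unstratified rejection rates were:
- equal timing: 5.1% and 5.3%
- 25% unscheduled, observation arm only: 6.5% and 6.3%
- 50% unscheduled, observation arm only: 8.7% and 8.5%
- pralatrexate scans 1, 2 and 4 weeks late: 11.1% and 10.6%; 13.0% and 12.2%; 8.1% and 7.5%

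Another check, also with 4,000 trials per scenario, gave 5.4% with equal timing, 6.2% at 20/40, 8.9% at 0/50 and 9.9% with the half-week gap. Power fell from 89.6% to 79.5% at 50/0.

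**5. The grouped analysis.** A CR/PR-stratified Prentice-Gloeckler test by visit number rejects in 4.9-5.7% in the null scenarios of step 3. It is not a general cure. With every scan in one arm 4 weeks late it rejects in 10.6-12.1% (log-rank 6.8-8.5%), and in 30-35% if late scans are assigned by date to the next visit.

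**The case against.** The best counter-argument is that this is stray text. The two sentences appear once and are absent from the synopsis and the SAP. No event count, alpha or decision rule rests on them. They may have been meant for a grouped method such as the one in SAP 8.5.5, though that is an inference. Imaging is scheduled identically in both arms and read blind. Pralatrexate patients attend more often for dosing, but B symptoms are recorded about every four weeks in both arms, and nothing shows that dosing visits would prompt scans. The moderate contrasts are small: 20/40 differs from 30/30 by 0.7 point, about two standard errors of the difference (√2 × 0.25 ≈ 0.35). Deaths would dilute the effect. With equal timing, stratifying does keep ordinary power (90.3% against 87.5% unstratified in the first check of step 4). The grouped analysis can itself do worse than the log-rank test.

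Most of this stands as a limit on size. It does not rescue the sentences, which concern asymmetric visits, the very setting in which they fail. Blinding the reader does not control when a scan is done in an open-label trial. SAP 8.5.5 leaves the analysis optional, does not define its trigger and gives no rule for late or unscheduled scans. Both documents defer central review details to a charter that is not available here, but a rule for assigning events to intervals belongs in the SAP.

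**Conclusion.** The concern holds: the assurances in Protocol 15.7.1 are wrong as written. That conclusion rests on the text and on how a stratified log-rank test works, not on the simulations.

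The practical size is uncertain. With equal timing there is no inflation to correct. Moderate differences in unscheduled detection put Type I error at 5.2-6.2%. One-sided detection of half the progressions, or a half-week mean gap within the allowed windows, puts it at 7.8-8.8%. Power could fall below the planned 80% only in the extreme 50/0 case among those examined. The unscheduled fractions, gaps and lags are all assumed. The text should be corrected because it describes the single PFS test on which continuation of the study and the OS test depend.

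**What to change.** - **Protocol 15.7.1:** delete the two sentences, or attach them in qualified form to a named grouped-data analysis.
- **SAP 8.5.5:** make the Prentice-Gloeckler analysis mandatory, stratified by CR/PR, with each progression assigned to its scheduled assessment interval.
- **Assignment rule:** a late scan keeps the number of the visit it was done for; an unscheduled progression goes to the next scheduled visit; only visits due before the data cut-off count.
- **Reporting:** show actual assessment times and unscheduled scans by arm beside this analysis.
- **Stated limits:** the grouped analysis is robust only when timing differences are small relative to the 12-week interval. It is a sensitivity analysis and leaves the primary log-rank gate and its Type I error as they are.

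The cost is wording in two documents and one analysis of data already collected. With equal timing the grouped analysis lost no power in the simulation (89.4% against 89.1%).

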### 15.7.2 Overall Survival

OS time is calculated as the number of days from randomization to the date of death, regardless of cause (date of death - date of randomization + 1). Survival follow-up will continue for up to 7 years from randomization.

The stratified log-rank test will be the primary method used to test the hypothesis that pralatrexate extends OS relative to observation. In addition, the OS HR, along with 95% CIs, will be estimated via the stratified Cox model. Strata used in these analyses will be those used for study randomization (as recorded using the IRT). Results of the unstratified Cox regression model (and log-rank test) will also be presented. The proportional hazards assumption of the Cox model will be assessed.

### 15.7.3 Objective Response Rate

The number and percentage of patients with an objective response of CR or PR will be summarized. The percentage will be calculated by dividing the number of patients within each category of response by the number of patients with measurable disease at baseline. Each patient will be counted within only 1 response group, with the overall best response during the study as the classification group. The treatment groups will be compared with respect to objective response rate (CR + PR) using the stratified Cochran-Mantel-Haenszel test. A 2-sided 95% exact CI will be calculated for the difference in objective response rates between the 2 treatment groups. Descriptive statistics will be provided for best tumor response for each treatment group.

## 15.8 Safety Analysis

Analysis of safety will be performed on the safety analysis set. Study data will be monitored on an ongoing basis by the clinical study team to ensure patients' safety.

### 15.8.1 Adverse Events

The Medical Dictionary for Regulatory Activities (MedDRA) will be used to code all AEs to a system organ class (SOC) and a preferred term. Patient incidence of AEs will be tabulated by SOC, preferred term, and severity grade for all AEs, SAEs, treatment-related AEs, and treatment-related SAEs. Each of these outputs will include tabulation by maximum severity for each SOC and preferred term as reported by the investigator based on CTCAE, Version 4.0. If an AE cannot be graded based on CTCAE, the investigator will assign a severity based on 1 = mild, 2 = moderate, 3 = severe, 4 = life threatening, and 5 = death related to AE. Summaries of AEs, SAEs, treatment-related AEs, and treatment-related SAEs occurring in at least 5% of the patients will be provided in descending order of frequency by SOC and preferred term.

Additional tables summarizing patient incidence (by preferred term) of the following will be generated:

- All AEs
- SAEs
- Treatment-related AEs
- Treatment-related SAEs
- Grade 3 or higher AEs
- AEs leading to the discontinuation of pralatrexate or observation or removal from study
- AEs leading to dose reductions of the study drug
- AEs with incidence  $\geq 5\%$
- Deaths

### 15.8.2 Adverse Events Grouped by Similar Preferred Term

Summary tables of treatment emergent, treatment-related, serious, and serious treatment-related AEs grouped by similar preferred term will be presented. For this presentation, certain similar preferred terms have been identified and will be coded to the same preferred term in order to present the event in a uniform manner. These terms are presented in the statistical analysis plan (additional preferred terms may be identified within each category during data review and added to this list).

Separate outputs will be provided for subgroups defined by age group (< 65, ≥ 65), gender, and race (if feasible).

Detailed listings for all AEs and listings and/or narratives will be provided for serious and significant AEs, and deaths (with 'on study' deaths [deaths that occur before the end of safety follow up period] identified).

### 15.8.3 Laboratory Parameters

Laboratory parameters for hematology and blood chemistry will be summarized at baseline and last observed value. Additionally, the maximum and minimum observed post baseline values will be summarized along with the change from baseline to the maximum observed value, minimum observed value, and last observed value. Tables of shifts in severity (CTCAE Version 4.0) from baseline for selected laboratory parameters and selected time-points may also be provided. A listing of all laboratory assessments may be provided.

Incidence of laboratory abnormalities and subject incidence of Grade 3 or 4 laboratory toxicities will be presented. Summaries of hematology and serum chemistry parameters along with grade shifts from baseline will be presented.

Standard PK parameters will be estimated from the limited plasma sampling (eg, AUC,  $C_{max}$ , and  $t_{1/2}$ ).

POPPK analyses will be conducted via nonlinear mixed-effects modeling to estimate POPPK parameters for pralatrexate, including typical values, inter-individual variation, and residual variability after administration of pralatrexate in the patient population, and to estimate the effects of individual-specific covariate factors (eg, demographics, disease state, etc) that may be predictive of the unexplained random variability in pralatrexate PK. In addition, the relationship between the PK of pralatrexate and response (safety and efficacy) will be explored.

## **16 STUDY MANAGEMENT**

### **16.1 Investigator Responsibilities**

#### **16.1.1 Good Clinical Practice**

The investigator will ensure that this study is conducted in full compliance with the principles of the “Declaration of Helsinki” (as amended in Tokyo, Venice, Hong Kong, and South Africa), ICH guidelines, or with the laws and regulations of the country in which the research is conducted. By signing the US Form FDA 1572, “Statement of Investigator”, the investigator commits to adhere to applicable sections of the US CFR parts 50 “Protection of Human Subjects”, 54 “Financial Disclosure by Clinical Investigators”, 56 “Institutional Review Boards”, and 312 subpart D “Responsibilities of Sponsors and Investigators”. All investigators will ensure adherence to ICH guidelines for GCP and Clinical Safety Data Management.

#### **16.1.2 IRB/EC/REB Approval**

The institution’s IRB/EC/REB, or other committee functioning in a similar capacity, will review and approve the protocol, initial and revised IC documents, protocol amendments, and safety items. After approval by the IRB/EC/REB, documentation of approval and the approved IC document will be sent to Allos/designee before any patient is enrolled into this study.

#### **16.1.3 Informed Consent**

The investigator is responsible for preparing the written IC document for this study. Allos or its designee will provide the investigator with templates for an IC document. The investigator may rearrange or reword the contents of these templates, or may add other elements or language, provided the meaning and content are not changed or deleted. Allos or designee must review and approve the IC document that is used by the investigator for this study prior to IRB/EC/REB submission.

Written IC will be obtained from all patients participating in this study, in accordance with ICH GCP and current regulatory requirements. The case history for each patient must document that the IC process was obtained prior to participation in the study. The original IC document will be kept in the patient’s record, and a copy will be provided to the patient.

